6.4 Withdrawal of individual subjects

Subjects can leave the study at any time for any reason if they wish to do so, without any consequences.

6.4.1 Specific criteria for withdrawal

Not applicable

6.5 Replacement of individual subjects after withdrawal

Not applicable

6.6 Follow-up of subjects withdrawn from treatment

These subjects will receive routine care from their treating physician.

6.7 Premature termination of the study

Not applicable

7. SAFETY REPORTING

7.1 Section 10 WMO event

In accordance to section 10, subsection 1, of the WMO, the investigator will inform the subjects and the reviewing accredited METC if anything occurs that makes the disadvantages of participation appear significantly greater than was foreseen in the research proposal. The study will be suspended, pending further review by the accredited METC, except insofar as suspension would jeopardise the subjects' health. The investigator will take care that all subjects are kept informed.

7.2 Adverse and serious adverse events

No specific serious adverse events are expected. Adverse events are defined as any undesirable experience occurring to a subject during the study, whether or not considered related to the surveillance protocol. All adverse events reported spontaneously by the subject or observed by the investigator or his staff will be recorded and reported to the coordinating investigator.

A serious adverse event is any untoward medical occurrence or effect that at any dose:

- results in death;
- is life threatening (at the time of the event);
- requires hospitalisation or prolongation of existing inpatients' hospitalisation;
- results in persistent or significant disability or incapacity;
- is a congenital anomaly or birth defect;
- is a new event of the trial likely to affect the safety of the subjects, such as an unexpected outcome of an adverse reaction, lack of efficacy of an IMP used for the treatment of a life threatening disease, major safety finding from a newly completed animal study, etc.

All SAEs will be reported by the coordinating investigator through the web portal *ToetsingOnline* to the accredited METC that approved the protocol, within 15 days after the sponsor has first knowledge of the serious adverse reactions.

SAEs that result in death or are life threatening should be reported expedited. The expedited reporting will occur not later than 7 days after the responsible investigator has first knowledge of the adverse reaction. This is for a preliminary report with another 8 days for completion of the report.

7.2.1 Suspected unexpected serious adverse reactions (SUSAR)

Not applicable

7.2.2 Annual safety report

Not applicable

7.3 Follow-up of adverse events

All adverse events will be followed until they have abated, or until a stable situation has been reached. Depending on the event, follow up may require additional tests or medical procedures as indicated, and/or referral to the general physician or a medical specialist.

7.4 Data Safety Monitoring Board (DSMB)

A special steering committee will be formed, consisting of an experienced gastroenterologist and surgeon, who will guard the safety and efficacy of the study protocol, in the light of possible new findings or data. The committee will report to the principal investigators and the medical ethics committee when they suspect a substantial advantage or disadvantage for certain groups of participants or surveillance strategies.

8. STATISTICAL ANALYSIS

The first analyses will concern the data collected within the first 3 years (until 2017). This report will contain purely descriptive statistics, according to the study endpoints described in 6.1. The thus obtained outcome data will be used as input for the MISCAN model. In addition, these data will be used to determine if the surveillance interval must be increased after 5 years of follow-up, to every 6 months, as was suggested in the consensus statement. The second analysis, after 10 years, will give an update of the first report and provide a more in depth analysis of the primary and secondary study endpoints.

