3. STUDY DESIGN

The study is designed as a prospective international multicenter cohort study, which will be coordinated by the department of Gastroenterology and Hepatology of the Erasmus University Medical Center of Rotterdam, the Netherlands. The study will run for ten years. Patients with a pancreatic cyst that requires surveillance will be included from September 2014 until August 2023. Follow-up will continue until August 2024. The first analysis will be conducted in September 2017, after three years, to provide data for the MISCAN model.

Figure 1; Study Flowchart

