4.4 Sample size calculation

In total, we aim to include 5000 patients during the study period of 10 years, of which 250 patients per year will be included in the Netherlands. This will provide over a 1000 patient years after three years, even in the case of expected loss to follow-up (15% of

patients included in the first year, 10% of those included in the second year, and 5% included in the third year). Internationally, depending on the number of cooperating centres throughout Europe, we expect to include between 250 and 500 patients yearly.

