6.3 Study procedures

After informed consent is obtained, the treating physician will receive online information regarding the surveillance strategy, as formulated in the consensus statement (Figure 2). Baseline characteristics will be filled out on the on-line CRF (patient and cyst characteristics, previous pancreatic surgery). The surveillance will take place at the hospital of origin. The treating physician will coordinate the surveillance. They will be reminded about follow-up dates by email.

Follow-up schedule and imaging studies

Follow-up is recommended at one-year intervals, except for newly diagnosed cysts with a diameter of ≥ 1 cm, for whom 6 months intervals are advised during the first year. According to the consensus statement, the follow-up frequency should increase after 5 years, to every 6 months. However, as this particular recommendation lacks all scientific justification, the decision to increase the follow-up frequency of the study population will not be made until 2017, after a preliminary analysis is performed.

Based on the consensus statement, cyst surveillance will be performed by MRCP. EUS will serve as an alternative, according to the preference of the treating physician. Switches in follow-up modality are permitted. The local radiologist is provided with instructions regarding the aspects that need to be addressed in the imaging report. If patients have more than one cyst, the specifications of the three largest cysts will be recorded and worrisome features will be monitored for all cysts.

To ascertain the reproducibility and quality of the MRI reports, 100 imaging studies will be selected at random and sent to the Erasmus Medical Center, for re-evaluation by a radiologist (TB). Discrepancies will be recorded and used to calculate the inter observer variability. For this reason, imaging studies should be stored at the hospital of origin. On request, during the study, this radiologist (TB) can be consulted for advice or a second opinion, in case of diagnostic difficulties.

Pathological analysis and tissue handling

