9.4 Benefits and risks assessment, group relatedness

Participation to the study does not cause any risk for patients, because the surveillance schedule does not differ from the present follow-up recommendations. The only possible burden may be the fact that two extra blood samples will be taken and that participants with a newly diagnosed cyst are invited to complete an online questionnaire. Completing the questionnaire will take no more than 5 to 15 minutes. Subjects may benefit from the active approach towards compliance to the cyst surveillance program. This will minimize the risk of patients getting lost to cyst follow-up.

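### A 3-year descriptive report is named as the basis for deciding follow-up frequency after 5 years, with the 5-year origin unstated and no in-study time beyond year 3

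*Protocol*

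**What the plan says.** - **Section 3:** "Patients with a pancreatic cyst that requires surveillance will be included from September 2014 until August 2023". Also: "The first analysis will be conducted in September 2017, after three years, to provide data for the MISCAN model".
- **Section 8:** the first analysis uses the data of the first three years. "This report will contain purely descriptive statistics, according to the study endpoints described in 6.1". The results feed the MISCAN model and, as a further use, "these data will be used to determine if the surveillance interval must be increased after 5 years of follow-up", to every 6 months as the consensus statement suggested.
- **Section 6.3:** the consensus statement calls for more frequent follow-up after 5 years. The protocol considers this step scientifically unjustified, so "the decision to increase the follow-up frequency of the study population will not be made until 2017, after a preliminary analysis is performed".
- **Section 4.4:** for 250 Dutch inclusions per year and stated losses, "This will provide over a 1000 patient years after three years". A further 250 to 500 patients per year are expected internationally.
- **Section 9.4:** participation carries no risk because "the surveillance schedule does not differ from the present follow-up recommendations".
- **Sections 4.2 and 8.1:** newly and previously diagnosed cysts are both eligible, and are described as separate sub-populations.

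**The concern.** The protocol fixes both the data cut (three years) and the question the data must settle (what happens after five). No analysis plan can add in-study follow-up beyond year 3 to a 2017 data set. If the rule is followed as written, a decision about late surveillance rests on early surveillance, or on patients whose time since diagnosis is not part of the stated basis.

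Three wording problems make this worse.

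- The origin of the 5 years is not given.
- Section 8 speaks of increasing the interval, section 6.3 of increasing the frequency. These are opposites, although the 6 months named in section 8 shows what is meant.
- Section 6.3 openly holds back one consensus recommendation, while section 9.4 rests its no-risk statement on the schedule matching the recommendations. Section 9.5 then reports an insurance dispensation granted because the study is without risks.

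Also at stake is which surveillance strategy the study can say it evaluated.

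**Working it through.** **1. Follow-up available in 2017.** First inclusion September 2014, first analysis September 2017 (section 3). Maximum study follow-up = 2017 − 2014 = 3.0 years. In-study patient-years beyond year 5 = 0. If the 5 years run from inclusion, the first participant reaches that point in September 2019 (2014 + 5), two years after the decision.

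**2. Reproducing the stated patient-years.** Inputs from section 4.4: 250 per year; losses of 15%, 10% and 5% for first-, second- and third-year entrants. Assumption: entry at mid-year, so 2.5, 1.5 and 0.5 years of follow-up.

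- Lost patients contribute nothing: 250 × (2.5 × 0.85 + 1.5 × 0.90 + 0.5 × 0.95) = 250 × 3.95 = 987.5.
- Lost patients contribute half their time: 250 × (2.5 × 0.925 + 1.5 × 0.95 + 0.5 × 0.975) = 250 × 4.225 = 1,056.

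The protocol's figure of over 1,000 is therefore reproduced from Dutch accrual alone. With international accrual the total is 500 to 750 per year, giving 500 × 3.95 = 1,975 to 750 × 3.95 = 2,963 patient-years, with lost patients contributing nothing.

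**3. Expected malignancies.** Section 1 derives the only annual rate in the protocol: 0.47 per 100,000 divided by 2.4% = 0.000196, rounded to 0.0002.

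| Patient-years | Expected events (× 0.0002) | Chance of none, exp(−expected) |
|---|---|---|
| 1,000 | 0.20 | 82% |
| 1,975 | 0.40 | 67% |
| 2,963 | 0.59 | 55% |

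**4. Precision if none is seen.** The exact Poisson 95% upper limit for zero events is 3.69 events, or 3.7 per 1,000 patient-years in 1,000 patient-years. That is more than 18 times the rate of 0.2 per 1,000 (3.69 / 0.2 = 18.4).

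**5. The two readings of the 5 years.**

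- *From inclusion:* the 2017 data contain nothing from the period in question. The deferral itself changes nobody's schedule before September 2019.
- *From diagnosis:* some participants may already be past 5 years, so some relevant time may exist. For those same participants, however, the consensus step is being withheld from entry, and the conflict with section 9.4 is immediate.

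Section 8.1 splits the cohort into new and previously diagnosed cysts, not by years since diagnosis.

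**The case against.** **Previously diagnosed cysts could inform the question.** This stands in part. A reader might infer that the 2017 data hold no information at all about the period after 5 years. The documents do not support that, because such patients are eligible and may be well past 5 years from diagnosis. Their number is unknown, and the protocol does not make time since diagnosis the basis of the decision. The surveillance flowchart (Figure 2) is not visible in the text at hand and might state the origin.

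**Malignancy is not the only outcome.** This stands. The report covers all endpoints in section 6.1, including indication for resection, which may be commoner, though no rate is given. The malignancy endpoint also includes high-grade dysplasia, so a registry rate of malignant cysts may understate it. More events within three years would still say nothing direct about in-study time after year 5.

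**The expected count could be higher.** A reader might infer that the protocol predicts up to 5 malignancies in 1,000 patient-years from the yield figure in section 1. It does not. That figure is a requirement for starting a programme, is stated per subjects followed rather than per year, and is itself inconsistent: 0.2% is 2 per 1,000, while 5 per 1,000 is 0.5%. Section 1 also cites 1 to 3% and 13%, but as prevalence or selected-series figures that it considers too high.

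**MISCAN will extrapolate.** Section 8 names the model as one use of the data and the follow-up decision as an additional one. It does not make the decision depend on the model.

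**Care stays with the treating physician.** This stands and limits the impact. The schedule is advisory (sections 5.2 and 6.3), the physician may intensify follow-up if parameters change (section 5.3), and a steering committee watches for disadvantage (section 7.4). It would be too strong to say that the report dictates care for the whole cohort.

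**Time scale and interval methods belong in an analysis plan.** Agreed. Their absence is not the point. The point is the data cut and the decision that the protocol itself fixes.

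**Conclusion.** The concern holds in a limited form and should be fixed. On the protocol's own dates, the report named as the basis for the post-5-year decision has at most 3.0 years of study follow-up and no in-study patient-years beyond year 5. Any information about that period must come from previously diagnosed cysts counted from diagnosis, in unknown number and under an origin the protocol does not state. At 0.0002 per year, fewer than one malignancy is expected, with or without international accrual: about 0.2 to 0.6.

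The timing result needs only the stated dates. The event counts assume mid-year entry, the stated losses with lost patients contributing nothing in the all-centre totals, and that the registry rate applies to the endpoint. The contradictions between sections 6.3 and 9.4, and between interval and frequency, are matters of text and need no assumption. How far the first affects participants before 2019 depends on the origin chosen.

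**What to change.** - Reconcile sections 6.3, 8 and 9.4 on whether the study schedule follows the consensus statement after 5 years, and use the same term for the change in sections 6.3 and 8. This review proposes no surveillance interval and no timing for the clinical decision.
- State the origin of the 5 years (diagnosis or inclusion) the same way throughout.
- In section 8, replace the claim that the 3-year report determines the post-5-year question with a statement of what that report can show.
- Report patient-years, events for both primary endpoints and exact Poisson confidence intervals by time since diagnosis, with delayed entry at inclusion, separately before and beyond 5 years. This needs the date of first diagnosis for every participant.

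**Cost:** protocol wording, one more analysis, and an acknowledgement that the 2017 data may not answer the question.

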8.1 Descriptive statistics

Baseline patient and cyst characteristics will be described (Table IV). Also, descriptive of the primary and secondary endpoints will be given. This will be performed for the total cohort and the following sub-populations: 1. unspecified cysts and suspected side-branch IPMN's, 2. newly and previously diagnosed cysts, and 3. cysts followed by EUS and MRCP. For each (sub)population, the follow-up duration, visit frequencies, and numbers lost-to-follow-up will be reported.

Depending on distributional properties of the observed variable, percentages, means \pm standard deviations (SD), or medians with interquartile ranges (IQR) will be reported. Statistical significance will be assessed with use of the Student's t-test for normally distributed continuous data; either the chi-square test for categorical data (with Yates' correction when appropriate) or Fisher exact test for categorical data; and the median test for non-normally distributed continuous data. All reported p-values will be two-sided and a value < 0.05 will be considered to be significant. Data will be analysed with SPSS 22 (or newer), Statistical Package for the Social Sciences (SPSS Inc, Chicago, Illinois).

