6. METHODS

6.1 Study endpoints

6.1.1 Main study endpoints

- The number of patients who reach an indication for pancreatic cyst resection, based on the criteria of the consensus statement (specified in Table I).
- The number of patients, diagnosed with a malignant cyst (either high-grade dysplasia or carcinoma).

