8.2 Univariate analysis

For the primary endpoints, univariate comparisons will be conducted, to identify individual patient and cyst risk factors for malignancy (Table IV). As primary potential risk factors are considered; 1. Cyst size, 2. Cyst growth, 3. Mural nodules/solid components, 4. increased serum CA 19.9, 5. Pancreatic duct dilatation, and 6. Patient age. Survival analysis techniques and Cox regression with time-dependent recurrent covariates measures will be applied to assess significance.

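### The primary yield is a number or percentage of patients with no time base, although follow-up will run from about 1 to 10 years, so the yield and its subgroup contrasts depend on length of follow-up

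*Protocol*

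**What the plan says.** Section 6.1.1 gives the first primary endpoint as "The number of patients who reach an indication for pancreatic cyst resection, based on the criteria of the consensus statement" and the second as "The number of patients, diagnosed with a malignant cyst (either high-grade dysplasia or carcinoma". Neither carries a time point or a person-time denominator.

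Section 8.1 then says: "Also, descriptive of the primary and secondary endpoints will be given". This applies to the total cohort and to three splits: unspecified cysts and suspected side-branch IPMN, then "2. newly and previously diagnosed cysts, and 3. cysts followed by EUS and MRCP". The summary measures listed are percentages, means and medians. Tests are listed by type of variable, with chi-square or Fisher for categorical data. The section also promises follow-up duration, visit frequency and losses for each group.

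Section 3 sets the calendar. On the early look at the data it says: "The first analysis will be conducted in September 2017, after three years, to provide data for the MISCAN model". On entry into the cohort it says: "Patients with a pancreatic cyst that requires surveillance will be included from September 2014 until August 2023". Observation of all patients, whenever they entered, closes one year after that, in August 2024.

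Section 8.2 names time-to-event methods for the primary endpoints, for the purpose of finding risk factors: "Survival analysis techniques and Cox regression with time-dependent recurrent covariates measures will be applied to assess significance". Section 8.3 adds multivariate survival analysis if there are more than 30 events, and expects that number for the primary endpoint.

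**The concern.** Establishing the yield of surveillance is the primary objective (section 2). With staggered entry and one common closing date, the percentage of included patients who have had an event mixes the event rate with the time each patient happened to be observed. It is not a risk over any stated period. It will rise between the 2017 and the final report even if nothing about the disease changes, and it cannot be set against a benchmark that has no period either.

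The same holds between subgroups. If newly and previously diagnosed cysts, or cysts followed by EUS and by MRCP, were recruited at different times or lost at different rates, their percentages would differ without any difference in rate. The first report is also meant to feed the MISCAN model and to inform the decision on follow-up frequency (section 8), so its headline figure should have a defined meaning.

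**Working it through.** **1. The plan's own figures.**
- Malignancy rate (section 1): 0.47 per 100,000 per year divided by a cyst frequency of 2.4% = 0.0000047 / 0.024 = 0.000196. The stated 0.0002 per year reproduces.
- Patient-years at three years (section 4.4): 250 Dutch patients per year, entering uniformly, have mean follow-up of 2.5, 1.5 and 0.5 years, with losses of 15%, 10% and 5%. If lost patients contribute half their time: 250 × (2.5 × 0.925 + 1.5 × 0.95 + 0.5 × 0.975) = 1056. If they contribute nothing: 250 × (2.5 × 0.85 + 1.5 × 0.90 + 0.5 × 0.95) = 987.5. The stated figure of over 1000 is reproduced on the first reading and missed by under 2% on the second. The sample size is thus argued in patient-years, while the yield is not.

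**2. Range of follow-up.** Entry in September 2014 gives about 10 years to August 2024; entry in August 2023 gives 1 year. At the first analysis in September 2017 the range is 0 to 3 years.

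**3. Crude yield under one constant rate λ.** At time t it is 1 − exp(−λt). Averaged over follow-up uniform on (a, b) it is 1 − [exp(−λa) − exp(−λb)] / [λ(b − a)]. Uniform entry, no losses. Only the first rate is the protocol's; the others are assumed.

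| Rate per year | At 1 y | First analysis (0–3 y) | Final analysis (1–10 y) | At 10 y |
|---|---|---|---|---|
| 0.02% | 0.02% | 0.03% | 0.11% | 0.20% |
| 0.1% | 0.10% | 0.15% | 0.55% | 1.00% |
| 0.5% | 0.50% | 0.75% | 2.70% | 4.88% |
| 1% | 1.00% | 1.49% | 5.32% | 9.52% |

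Within each row the rate is the same throughout. In the first row the yield is a tenth of the 0.2% benchmark or level with it, depending only on follow-up. Section 1 also glosses the benchmark as 5 per 1000, which is 0.5%. At 0.1% per year the first analysis lies below both figures and the final one above both. Expressed as a rate, the first row is 0.2 per 1000 patient-years at either analysis.

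**4. Which rate is plausible.** With 5000 patients and mean potential follow-up of 5.5 years there are at most 5000 × 5.5 = 27,500 patient-years. At 0.0002 per year that gives 5.5 malignancies. The 30 events of section 8.3 would need 30 / 27,500 = 0.0011, or about 0.1% per year. The protocol gives no rate for reaching a resection indication.

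**5. Subgroup contrasts with equal true rates.** Simulation, 2000 runs, two groups of 2500, exponential event times, two-sided 0.05. The split, rates and follow-up spans are assumptions. Each cell gives the share of significant results for the Yates chi-square on percentages, then for an exact test on events per person-time.

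| Mean follow-up | 0.1% per year | 0.5% per year | 1% per year |
|---|---|---|---|
| 6.5 v 4.5 y | 11% / 4.1% | 52% / 4.1% | 83% / 4.6% |
| 7.75 v 3.25 y | 49% / 3.6% | 99.9% / 3.9% | 100% / 5.0% |

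A smaller imbalance does less. At 6 v 5 years the normal-approximation figures for the comparison of percentages are 7%, 18% and 32%. At the protocol's malignancy rate, 6.5 v 4.5 years gives about 2500 × 0.0002 × 6.5 = 3.25 v 2.25 expected events, too few for a false difference to matter much.

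**The case against.** The strongest reply is that the protocol does not say the primary endpoints will be compared by chi-square. A reader might infer it, because the test list follows the subgroup description in section 8.1. But that list is general, sorted by variable type, and the preceding text also covers baseline characteristics and secondary endpoints. Where comparisons of the primary endpoints are named, in section 8.2, the methods are survival analysis and Cox regression. The first report is to be purely descriptive. This stands, so the testing part of the point is conditional.

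It does not remove the rest. The six primary factors in section 8.2 include neither surveillance modality nor newly or previously diagnosed status. Table IV does not list modality either, and comes no closer to the other split than a history of pancreatic cyst or cancer. No other test is named for the section 8.1 splits. Even with no test at all, the yield has no time base. Reporting follow-up duration and losses per group would reveal an imbalance but not correct for it.

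A second reply is that the size of any false difference rests on chosen inputs. That also stands: the protocol gives no rate for resection indications, no subgroup sizes and no follow-up by subgroup. A striking example is easy to build at 2% per year, but that is 100 times the protocol's malignancy rate.

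Finally, detail such as the interval method or the choice of time points may properly sit in an analysis plan that is not shown. The point is confined to what the protocol itself fixes: the endpoint as a number and its summary as a percentage.

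**Conclusion.** The point holds for the headline yield and, conditionally, for the section 8.1 subgroup contrasts. As written, the yield depends on follow-up. At a constant 0.0002 per year it moves from about 0.03% at the first analysis to about 0.11% at the final one, and from 0.02% to 0.20% between 1 and 10 years. This assumes uniform entry and no losses. If chi-square or Fisher is applied to the subgroup percentages, equal rates can yield false differences: with 2500 v 2500 and mean follow-up of 6.5 v 4.5 years, about 11% of the time at 0.1% per year and 83% at 1%, all assumed.

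Three stronger readings are not supported:
- **Benign resection as the end of malignancy risk.** Section 6.1.2 follows cyst recurrence after resection, and section 6.3 monitors worrisome features in all of a patient's cysts.
- **An overstated Kaplan-Meier risk passed to MISCAN.** No section plans a Kaplan-Meier estimate of the yield.
- **A required analysis on time since diagnosis with delayed entry.** The original diagnosis date of previously diagnosed cysts is not listed among the data collected (sections 5.4 and 6.3, Table IV).

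**What to change.** Reword section 8.1 so that each primary endpoint is reported, for the cohort and each subgroup, as events per 1000 patient-years with a 95% CI and as cumulative incidence at times fixed in advance, chosen so that enough patients remain under observation. Death may be treated as a competing event in the cumulative incidence. Keep the counts and percentages as description. State that any tested section 8.1 subgroup contrast on a primary endpoint uses the time-to-event methods already named in section 8.2, not chi-square or Fisher. If the result is to be read against the section 1 benchmark, state the period that the benchmark covers.

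The cost is a few sentences and slightly more analysis. Entry and exit dates are already needed for the follow-up durations in section 8.1, and event dates for the survival analyses in section 8.2.

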1. INTRODUCTION AND RATIONALE

Incidental pancreatic cysts are prevalent, in particular in this day and age of cross-sectional imaging[3]. The reported incidence depends on the applied imaging technique and the investigated setting. In CT series of symptomatic patients, the incidence varies from 1 to 3%[4]. In healthy individuals undergoing a screening MRI, we found a pancreatic cyst in 2.4%[5]. An autopsy series by Kimura even reported a prevalence rate of 24%[6].

These cysts form a heterogeneous group of non-neoplastic and neoplastic lesions, with variable pathologic features, clinical presentation, and outcome. Most cysts are (virtually) benign, such as Pseudocysts and Serous Cystadenomas (SCA), and, when asymptomatic, do not require treatment or follow-up. However, some neoplastic cysts have a malignant potential (Mucinous cysts and Intraductal Papillary Mucinous Neoplasms (IPMN)), and require follow-up or even a surgical resection[7, 8]. Unfortunately, to distinguish these pancreatic cysts, especially the smaller ones, is often impossible[9].

A second problem in pancreatic cyst management is that data regarding the natural history and predictive factors for malignant degeneration are virtually lacking.[2, 10]. The literature is biased by highly selected patients series from tertiary referral centres. Sahani reported a 13% risk of malignancy in cysts smaller than 3 cm[2]. In asymptomatic cysts, the reported prevalence of carcinoma varies between 1 and 3%[8]. However, the malignant potential is likely to be much lower, considering the high prevalence of pancreatic cysts and the low incidence of malignant cystic neoplasms. Fitzgerald, for instance, reported a yearly incidence of malignant pancreatic cysts from a state-wide tumour registry in Michigan, USA, of 0.47/100.000[7]. Given the 2.4% incidence of pancreatic cysts on screening MRI's, the calculated malignancy rate would be no more than 0.0002 per year[5].

Because it is impossible to estimate the cancer risk of small pancreatic cysts, treating physicians face a difficult dilemma: to miss a pancreatic carcinoma, or to expose the majority of patients with a benign cystic lesion to redundant investigations, or even unnecessary surgery (with substantial morbidity and mortality). At present, an intensive surveillance strategy is generally chosen, driven out of fear for one of the most deadly cancers.

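### Section 8.1 names the pooled-variance Student's t-test for non-randomised sub-populations; its 5% level fails if groups differ in both size and variance, and Welch's test avoids this at almost no cost (minor improvement)

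*Protocol*

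**What the plan says.** Protocol section 8.1 asks for descriptive results in the whole cohort and in three pairs of sub-populations: "1. unspecified cysts and suspected side-branch IPMN's, 2. newly and previously diagnosed cysts, and 3. cysts followed by EUS and MRCP". It then fixes the tests. For continuous variables judged normal: "Statistical significance will be assessed with use of the Student's t-test for normally distributed continuous data". Other continuous variables go to a median test and categorical ones to chi-square or Fisher tests. The threshold is general: "All reported p-values will be two-sided and a value < 0.05 will be considered to be significant".

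Section 8.1 does not list which comparisons will be tested. The three sub-population pairs are the natural reading, since they are the only groupings it names.

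On group sizes, section 4.4 gives only the total: "In total, we aim to include 5000 patients during the study period of 10 years". On imaging modality, section 6.3 bases surveillance on MRCP and adds: "EUS will serve as an alternative, according to the preference of the treating physician". Section 6.2 records that randomisation does not apply.

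For risk factors for malignancy, section 8.2 names a different method: "Survival analysis techniques and Cox regression with time-dependent recurrent covariates measures will be applied to assess significance".

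**The concern.** Student's t-test estimates one common variance from both groups. When group sizes differ, that estimate mostly reflects the larger group. If the smaller group is in fact more variable, the standard error is too small and p < 0.05 occurs too often. If it is less variable, the standard error is too large and real differences are missed.

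Nothing in this design pushes the groups towards equal size or equal spread, because membership follows diagnosis, referral history or physician preference. EUS versus MRCP is the pair where the text itself makes imbalance plausible. For new versus previously diagnosed cysts there is a plausible source of unequal spread. Section 6.3 sets two first-year visit schedules among new cysts, depending on size, and one schedule for the rest; section 8.1 reports visit frequency by sub-population. Whether that variable would be treated as normal is open.

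At stake is whether the stated 0.05 means 5% in these comparisons.

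**Working it through.** **Inputs from the protocol.** Two-sided level 0.05 and pooled t-test (8.1); total 5000 (4.4).

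**Inputs assumed, because the protocol gives none.** The share p of patients in the smaller group, and the ratio r of the smaller group's SD to the larger group's SD.

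**Formula.** Set the larger group's SD to 1. The pooled test uses the variance V_pooled = [((n1−1)r² + (n2−1))/(n1+n2−2)] × (1/n1 + 1/n2). The correct variance is V_true = r²/n1 + 1/n2. In large samples

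V_pooled / V_true ≈ [p r² + (1−p)] / [(1−p) r² + p]

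and the true level is 2 × [1 − Φ(1.96 × √(V_pooled/V_true))].

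**Reproducing the stated level first.** The ratio equals 1 exactly when (2p−1)(r²−1) = 0, that is, when p = 0.5 or r = 1. The true level is then 5.0%, even at r = 2 with a 1:1 split, or at any split with equal SDs. Both conditions must fail before the level moves. Total sample size drops out, so a large cohort does not cure the problem.

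**Small group 10% (500 versus 4500).**

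| r | V_pooled/V_true | √ | 1.96 × √ | True level |
|---|---|---|---|---|
| 0.8 | 0.964/0.676 = 1.426 | 1.194 | 2.341 | 1.9% |
| 1.0 | 1 | 1 | 1.960 | 5.0% |
| 1.25 | 1.056/1.506 = 0.701 | 0.837 | 1.641 | 10.1% |
| 1.5 | 1.125/2.125 = 0.529 | 0.728 | 1.426 | 15.4% |
| 2.0 | 1.300/3.700 = 0.351 | 0.593 | 1.162 | 24.5% |

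**Other shares.**

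| Share of small group | r = 1.5 | r = 2 |
|---|---|---|
| 20% | 12.1% | 17.9% |
| 30% | 9.3% | 12.5% |
| 40% | 7.0% | 8.2% |
| 50% | 5.0% | 5.0% |

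For example, at 30% and r = 1.5: 1.375/1.875 = 0.733, root 0.856, times 1.96 = 1.678, giving 9.3%.

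**Simulation (20,000 runs per setting).**

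| Split | r | Student | Welch |
|---|---|---|---|
| 100:900 | 1.5 | 15.5% | 5.1% |
| 100:900 | 2 | 24.1% | 4.9% |
| 200:800 | 1.5 | 12.1% | 4.9% |
| 300:700 | 1.5 | 9.5% | 5.2% |

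Over 13 settings (small-group shares 3% to 50%, r from 0.5 to 2), Welch's test stayed between 4.8% and 5.2%.

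**Cost of Welch's test if variances are equal.** When the small group is a small part of the total, Welch's degrees of freedom are close to n1 − 1. Take a true difference of 2.68 standard errors. Student's test has power Φ(2.68 − 1.96) = Φ(0.72) = 76.4%. With n1 = 30 the critical value is about 2.045, so power is Φ(0.635) = 73.7%, a loss of about 3 points. With n1 = 100 it is about 1.984, so power is Φ(0.696) = 75.7%, a loss of less than 1 point.

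**The case against.** The strongest reply is that nothing in the protocol shows the two harmful conditions occurring together. This stands. No sub-population size and no SD is given. Nothing suggests imbalance in the unspecified versus side-branch IPMN pair or in the new versus previously diagnosed pair. For EUS versus MRCP, the choice follows physician preference and switching is allowed. For variables such as age or BMI, a two-fold difference in SD between the EUS and MRCP groups is hard to believe.

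A reader might infer that the nominal 5% is really 20 to 30% in this study. The protocol does not support that: in the cases worked here, such levels appear only at an SD ratio of 2 together with a small group of about 10% or less.

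A reader might also extend the point to malignant versus non-malignant cysts, which would be very unequal groups given the 1 to 3% carcinoma prevalence quoted in section 1. But section 8.2 assigns that question to survival methods and Cox regression. Operated versus non-operated patients are not among the groupings in 8.1 either.

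It can further be said that no main conclusion rests on these p-values. The primary endpoints are patient counts (6.1.1), the three-year report is descriptive and supplies outcome data to the MISCAN model (8), and questionnaire changes over time use multilevel models (8.3). This too stands, and it limits the weight of the point.

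Finally, the choice between pooled and Welch could be left to a statistical analysis plan. That answers less, because 8.1 does not leave it open: it names the test and the threshold.

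**Conclusion.** The point holds as a conditional, low-severity improvement; it is not a demonstrated error. The named test does not protect the 5% level when sub-populations differ in both size and variance, and the design rules out neither. The size cannot be fixed from the protocol. For a 10% small group it is about 2% to 10% at SD ratios of 0.8 to 1.25, rising to 15% at 1.5 and 25% at 2. For a 30% small group it is about 9% at a ratio of 1.5. All shares and SD ratios here are assumptions. Unequal size alone does no harm.

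The consequence is confined to the sub-population comparisons of approximately normal variables in 8.1. The primary endpoints, the Cox analysis of malignancy risk factors and the MISCAN inputs are not affected.

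**What to change.** In section 8.1, replace *Student's t-test* by *Welch's unequal-variance t-test* for two-group comparisons of normally distributed continuous variables, and state that the confidence interval for the difference comes from the same method. Fix this as the default, with no preliminary test of variances.

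The cost is one phrase, with no new data and no change in sample size. If variances are in fact equal, about 3 points of power are lost with some 30 patients in the smaller group and less than 1 point with 100.
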